9.4. Treatment Accountability and Compliance

The patients will receive the study drug at the site directly from the Investigator or designee who will also give instruction for dose administration. The date of study drug dispensed to the patients will be recorded in eCRF and patient's source document. At all site visits, patients will return all study drug, including packaging, dispensed at the previous visit.

The dose of study drug and study patient identification will be confirmed at the time of administration by a member of the study site staff other than the person administering the study drug.

When patients self-administer the study drug at home, compliance with the protocol will be assessed at each visit. Compliance will be assessed by direct questioning and counting returned tablets during the site visits and documented in the source documents and relevant form. Deviation from the prescribed dosage regimen should be recorded.

A record of the quantity of study drug dispensed to and administered by each patient must be maintained and reconciled with study drug and compliance records. Study drug administration dates, including dates for administration delays and/or dose reductions will also be recorded.

9.5. Prior and Concomitant Therapy

Any concomitant medication, supplement, or procedure within 6 months prior to Baseline or receives during the study must be recorded along with:

- Reason for use
- Dates of administration including start and end dates
- Dosage information including dose and frequency

Patients may take any medication that is not restricted by the protocol and would not be expected to interfere with the conduct of the study or affect assessments. Chronic medication should be dosed on a stable regimen.

9.5.1. Allowed Treatments and Rescue Medications

All medications (prescription and nonprescription), treatments and therapies taken from Screening throughout their entire participation in the study, including those initiated prior to the start of the study, must be recorded on the patient's source document and on the appropriate page of the eCRF. The dose, unit, frequency, route, indication, date the medication was started and the date the medication was stopped (if not ongoing) must be recorded. The recording of any permitted topical medications taken for psoriasis should also include the area of the body to which they are applied and the frequency of application.

The following topical therapies will be permitted during the study:

• For psoriasis body lesions: nonmedicated emollients or low potency corticosteroids used only for treatment of the face, axillae, and groin

Examples of low potency corticosteroids (Groups VI and VII):

- o Betamethasone valerate lotion 0.05%
- o Desonide cream 0.05%
- o Fluocinolone acetonide solution 0.01%
- o Dexamethasone sodium phosphate cream 0.1%
- o Hydrocortisone lotion, cream, or ointment 2.5%
- Hydrocortisone acetate cream 1%
- o Methylprednisolone acetate cream 0.25%
- For scalp psoriasis lesions: coal tar shampoos and/or salicylic acid scalp preparations but only if on a stable use since Screening

Topical preparations should not be applied within 24 hours of the clinic visit.

9.5.2. Prior and Concomitant Medications

Restricted prior therapies are provided in Table 3. In addition, patients with any prior treatment with orismilast or failure of treatment with apremilast or any other systemic PDE4 inhibitor are ineligible.

Table 3. Disallowed therapies and treatments

Compound	Washout
Topical medications/treatments that could affect psoriasis or study evaluations (eg, corticosteroids, anthralin, calcipotriene, vitamin D derivatives, retinoids, tazarotene, pimecrolimus, tacrolimus, or PDE4 inhibitor)	Within 2 weeks prior to Baseline and throughout the study
Systemic treatment with therapies other than biologics with a possible effect on psoriasis like apremilast, corticosteroids, retinoids, systemic immunosuppressants (eg, methotrexate, azathioprine, cyclosporine), protein	Within 4 weeks prior to Baseline or 5 half-lives (whichever is longer) and throughout the study

Compound	Washout
kinase inhibitors (eg, tofacitinib, baricitinib, or upadacitinib) or fumaric acid	
Investigational drugs other than the study drug	Within 4 weeks of randomization, or 5 half-lives, if known (whichever is longer) and throughout the study
Initiation of or changes of doses to concomitant medication that could exacerbate psoriasis (for example, beta blockers, angiotensin-converting enzyme inhibitors, antimalarial drugs, lithium)	Within 4 weeks prior to Baseline and throughout the study
Use of phototherapy or prolonged sun exposure or use of tanning booths or other ultraviolet light sources (ie, UVB, psoralens and long-wave ultraviolet radiation)	Within 4 weeks of Baseline and throughout the study
Etanercept	Within 8 weeks prior to Baseline and throughout the study
TNF inhibitors like adalimumab, certolizumab pegol, or infliximab	Within 12 weeks prior to Baseline and throughout the study
Any biologic agents targeting IL-12, IL-17, or IL-23 like ustekinumab, secukinumab, brodalumab, guselkumab, ixekizumab, risankizumab, or tildrakizumab	Within 16 weeks prior to Baseline and throughout the study
Rituximab and any B-cell depleting agent	Within 24 weeks prior to Baseline and throughout the study
Concomitant medication mainly metabolized via cytochrome 2D6 isozyme and with narrow therapeutic window such as tricyclic antidepressants (e.g., nortriptyline, amitriptyline, imipramine, desipramine) or Type 1C antiarrhythmics (propafenone, flecainide and encainide) or via cytochrome 3A4 with a narrow therapeutic index	4 weeks prior to Baseline and throughout the study

Abbreviations: IL, interleukin; PDE4, phosphodiesterase-4; TNF, tumor necrosis factor alpha

Concomitant medication mainly metabolized via cytochrome 3A4 and with narrow therapeutic window (such as anticoagulant or digoxine) are not to be excluded but require close medical monitoring.

The Medical Monitor should be contacted for questions regarding concomitant or prior therapy.

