8.2. Exclusion Criteria

Patients are excluded from the study if any of the following criteria apply:

1. Therapy-resistant psoriasis defined as ≥2 treatment failures due to inadequate efficacy within the past 5 years of any biologic therapies (including but not limited to etanercept,

adalimumab, infliximab, certolizumab pegol, guselkumab, secukinumab, risankizumab, ixekizumab, tildrakizumab, or ustekinumab) administered in adequate dose and duration according to the label or local/national guidelines (patients who stopped systemic treatment for reasons not related to lack of efficacy are not excluded).

- 2. Unstable psoriasis or PsA with acute deterioration within 4 weeks of the Screening visit.
- 3. History of allergy or hypersensitivity to any component of the study treatment.
- 4. Active infection (eg, bacteria, viral, fungal) requiring treatment with systemic antibiotics within 4 weeks of the Screening visit.
- 5. Malignancy or history of malignancy except for treated (ie, cured) basal cell skin carcinomas.
- 6. Current diagnosis of predominant guttate, erythrodermic, exfoliative, or pustular psoriasis, or of drug-induced psoriasis, or other skin conditions that might confound the evaluation of psoriasis vulgaris, as judged by the Investigator (eg, AD, lupus).
- 7. Any recurrent medical condition associated with serious GI diseases, such as inflammatory bowel disease.
- 8. Any medical or psychiatric condition (eg, current major depression with a score for depressive symptoms ≥15 of HADS at Baseline, schizophrenia, suicidal behavior, psychiatric hospitalization within the prior year) which, in the Investigator's opinion, would preclude the patient from adhering to the protocol, completing the study per protocol, and/or would place the patient at unacceptable risk for receiving the investigational therapy.
- 9. Any therapies and systemic treatments as described in Table 3 which do not comply with the indicated washout interval.
- 10. Any previous treatment with orismilast or failure of treatment with apremilast or any other systemic PDE4 inhibitor as described in Table 3.
- 11. Any condition, including laboratory or ECG abnormalities, that places the patient at unacceptable risk to participate in the study or confounds the ability to interpret data from the study.
- 12. Severe hepatic impairment based upon medical history and laboratory abnormalities (eg, low albumin and abnormal bilirubin).

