9.5.3. Drug-Drug Interactions

From clinical studies, orismilast can be considered a mild inhibitor of CYP3A4/5, and systemic exposure to medicinal products metabolized by CYP3A4 may be increased when coadministered with orismilast. Concomitant use of orismilast with CYP3A4 substrates may

increase the systemic exposure to these medicinal products. Patients receiving orismilast concurrently with these medicinal products should be monitored for related AEs especially if they have a narrow therapeutic window. Refer to the following link for examples of clinical inhibitors for P450-mediated metabolisms: https://www.fda.gov/drugs/drug-interactions-labeling/drug-development-and-drug-interactions-table-substrates-inhibitors-and-inducers#table3-2.

In vitro orismilast is a competitive direct inhibitor of CYP2D6. Concomitant use of orismilast with other drugs mainly metabolized by cytochrome CYP2D6 has not been studied clinically. Because of a potential increase of systemic exposure to medicinal products metabolized by CYP2D6 when concomitantly administered with orismilast patients should be monitored for AEs related to these medicinal products. Co-administration of drugs with a narrow therapeutic index such as tricyclic antidepressants (e.g., nortriptyline, amitriptyline, imipramine, desipramine) or Type 1C antiarrhythmics (propafenone, flecainide and encainide) is prohibited (see Table 3).

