#### 4.2.2. Exclusion Criteria

Patients are excluded from the study if any of the following criteria apply:

1. Therapy-resistant psoriasis defined as  $\geq 2$  treatment failures due to inadequate efficacy within the past 5 years of any biologic therapies (including but not limited to etanercept, adalimumab, infliximab, certolizumab pegol, guselkumab, secukinumab, risankizumab, ixekizumab, tildrakizumab, or ustekinumab) administered in adequate dose and duration according to the label or local/national guidelines (patients who stopped systemic treatment for reasons not related to lack of efficacy are not excluded).
2. Unstable psoriasis or PsA with acute deterioration within 4 weeks of the Screening visit.
3. History of allergy or hypersensitivity to any component of the study treatment.
4. Active infection (eg, bacteria, viral, fungal) requiring treatment with systemic antibiotics within 4 weeks of the Screening visit.
5. Malignancy or history of malignancy except for treated (ie, cured) basal cell skin carcinomas.
6. Current diagnosis of predominant guttate, erythrodermic, exfoliative, or pustular psoriasis, or of drug-induced psoriasis, or other skin conditions that might confound the evaluation of psoriasis vulgaris, as judged by the Investigator (eg, atopic dermatitis, lupus).
7. Any recurrent medical condition associated with serious GI diseases, such as inflammatory bowel disease.
8. Any medical or psychiatric condition (eg, current major depression with a score for depressive symptoms  $\geq 15$  of HADS at Baseline, schizophrenia, suicidal behavior, psychiatric hospitalization within the prior year) which, in the Investigator's opinion, would preclude the patient from adhering to the protocol, completing the study per protocol, and/or would place the patient at unacceptable risk for receiving the investigational therapy.
9. Any therapies and systemic treatments as described in Protocol Section 9.5.2 which do not comply with the indicated washout interval. [REDACTED].
10. Any previous treatment with orismilast or failure of treatment with apremilast or any other systemic PDE4 inhibitor as described in Protocol Section 9.5.2.
11. Any condition, including laboratory or ECG abnormalities, that places the patient at an unacceptable risk to participate in the study or confounds the ability to interpret data from the study.
12. Severe hepatic impairment based upon medical history and laboratory abnormalities (eg, low albumin and abnormal bilirubin).

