## **8.6. Medication**

The WHO Drug, March 2021, B3 will be used to classify prior and concomitant medications by therapeutic class and drug name.

Prior medication is defined as any medication taken before the date of the first dose of study treatment. Concomitant medication is defined as any medication taken on or after the date of the first dose of study treatment.

The use of prior medications, concomitant medications and concomitant disallowed medications will be summarized by the number and percentage of patients for the ITT population. If a patient takes a specific medication multiple times or takes multiple medications within a specific therapeutic class, that patient would be counted only once for the coded drug name or therapeutic class.

Prior and concomitant medications will be listed for all patients in the randomized population.

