## 18. Index of Tables

Header	Table Number	Name	Analysis Population
14.		TABLES AND FIGURES	
14.1		Demographic Data	
14.1.1		Patient Disposition	
	14.1.1.1	Screen Failure Reasons	Screened Patients
	14.1.1.2.1	Analysis Populations	Screened Patients
	14.1.1.3.1	Patient Disposition	Randomized Population
14.1.2		Protocol Deviations	
	14.1.2.1	Protocol Deviations	Randomized Population
14.1.3		Demographic and Baseline Characteristics	
14.1.3.1		Patient Demographic and Baseline Characteristics	
	14.1.3.1.1	Demographic and Baseline Characteristics	ITT Population
	14.1.3.1.2	Demographic and Baseline Characteristics	PP Population
	14.1.3.1.3	Previous Psoriasis Treatments	ITT Population
	14.1.3.1.4.1	Baseline Efficacy Assessments	ITT Population
	14.1.3.1.4.2	Baseline Efficacy Assessments	PP Population
14.1.3.2		Baseline Disease Characteristics	
	14.1.3.2	Smoking and Alcohol History	ITT Population
14.1.3.3		Medical History	
	14.1.3.3.1	Medical History	ITT Population
	14.1.3.3.2	Ongoing Conditions	ITT Population
14.1.4		Medications	
	14.1.4.1	Prior Medication	ITT Population
	14.1.4.2	Concomitant Medication	ITT Population
	14.1.4.3	Concomitant Disallowed Medication	ITT Population
14.1.5		Treatment Compliance	
	14.1.5.1	Compliance - Overall	ITT Population
	14.1.5.2	Compliance - During the Titration Period	ITT Population
14.2		Efficacy Data	
14.2.1		Primary Efficacy Parameters	
	14.2.1.1.1	Percentage Change in Psoriasis Activity and Severity Index (PASI) Score from Baseline at Week 16 Primary Efficacy Analysis: ANCOVA - Multiple Imputation	ITT Population
	14.2.1.1.2	Percentage Change in Psoriasis Activity and Severity Index (PASI) Score from Baseline at Weeks 20, 12, 8 and 4 Primary Efficacy Analysis: ANCOVA - Multiple Imputation	ITT Population
	14.2.1.1.3	Percentage Change in Psoriasis Activity and Severity Index (PASI) Score from Baseline at Week 16 Primary Efficacy Analysis: ANCOVA – Multiple Imputation	PP Population
	14.2.1.1.4	Percentage Change in Psoriasis Activity and Severity Index (PASI) Score from Baseline at Weeks 20, 12, 8 and 4 Primary Efficacy Analysis: ANCOVA – Multiple Imputation	PP Population

This document is confidential.

Header	Table Number	Name	Analysis Population
	14.2.1.1.5	Actual Values, Change from Baseline and Percentage Change from Baseline in Psoriasis Activity and Severity Index (PASI) Score Primary Efficacy Analysis: Descriptive Statistics– Observed Cases	ITT Population

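### Protocol 9.5.2 both disallows and permits CYP3A4-metabolised drugs with a narrow therapeutic margin, so eligibility and the disallowed-medication flag rest on two opposite rules

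*Protocol*

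**What the plan says.** The last row of Protocol Table 3 (section 9.5.2, disallowed treatments) begins with drugs metabolised mainly by CYP2D6, giving tricyclic antidepressants and Type 1C antiarrhythmics as examples, and then continues "or via cytochrome 3A4 with a narrow therapeutic index". The restriction runs from four weeks before Baseline to the end of the study.

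After only the abbreviation line, the next sentence says that drugs metabolised mainly via "cytochrome 3A4 and with narrow therapeutic window (such as anticoagulant or digoxine) are not to be excluded but require close medical monitoring". The line after it reads "The Medical Monitor should be contacted for questions regarding concomitant or prior therapy".

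The CYP3A4 paragraph of Protocol 9.5.3 says that patients taking CYP3A4 substrates together with orismilast "should be monitored for related AEs especially if they have a narrow therapeutic window". The only prohibition stated in 9.5.3, with a reference to Table 3, is in its CYP2D6 paragraph.

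Exclusion criterion 9 in Protocol 8.2 excludes "Any therapies and systemic treatments as described in Table 3 which do not comply with the indicated washout interval". The SAP version (4.2.2) reads "Any therapies and systemic treatments as described in Protocol Section 9.5.2 which do not comply with the indicated washout interval". On reporting, SAP 8.6 says that "concomitant disallowed medications will be summarized by the number and percentage of patients for the ITT population".

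**The concern.** The row and the sentence describe the same class of drug and give opposite instructions. A site could turn a patient away under Table 3, or enrol that patient with monitoring under the sentence below it, and cite the protocol correctly either way. With about 40 centres planned, practice could differ between sites.

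The rule concerns safety as well as eligibility. Protocol 5.2.2.1 reports that midazolam exposure with orismilast 30 mg twice daily was 132% (AUC) and 137% (Cmax) of that with midazolam alone, and classes orismilast as a weak CYP3A4 inhibitor. Section 9.5.3 warns that exposure to CYP3A4 substrates may rise.

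For the analysis, the question is whether such a drug counts as disallowed. Without one rule, the flag in the dataset depends on which sentence the programmer or data reviewer read.

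**Working it through.** No arithmetic applies. The check is to set the texts side by side and follow each rule to its consequences.

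**The texts**

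| Place | Drugs covered | Instruction |
|---|---|---|
| Protocol 9.5.2, Table 3, last row, closing clause | CYP3A4-metabolised, narrow therapeutic *index* | Disallowed from four weeks before Baseline and during the study |
| Protocol 9.5.2, sentence below Table 3 | Mainly CYP3A4-metabolised, narrow therapeutic *window* | Not excluded; close monitoring |
| Protocol 9.5.3, CYP3A4 paragraph | CYP3A4 substrates, with emphasis on a narrow *window* | Monitoring during concurrent use |
| Protocol 9.5.3, CYP2D6 paragraph | CYP2D6-metabolised, narrow *index* | Prohibited; agrees with Table 3 |

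**Step 1: do *index* and *window* separate two classes?** No. Table 3 uses *window* for the tricyclics and Type 1C antiarrhythmics, and 9.5.3 uses *index* for the same drugs. The protocol treats the words as interchangeable.

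**Step 2: is the lower sentence an exception to the row?** Nothing in the wording makes it one. Its named drugs are introduced as examples, not as a closed list, and it covers the whole class. Read as an exception, it would leave the CYP3A4 clause of the row with nothing to disallow.

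**Step 3: is the point settled elsewhere?** The amendment summaries in Protocol Appendix 1 do not mention it. SAP exclusion criterion 9 refers to Protocol 9.5.2 as a whole, which contains both rules. Protocol section 15 lets the SAP prevail where the two differ, but the visible SAP text states no rule of its own. Text is redacted directly after SAP criterion 9, so this statement is limited to what can be read.

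**Step 4: follow one patient through both rules.** Take a patient on a qualifying CYP3A4 drug at Screening who continues it.

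| | Under the Table 3 row | Under the sentence below it |
|---|---|---|
| Exclusion criterion 9 | Washout not met; ineligible | No exclusion on this ground |
| If randomised: Listing 16.2.3.1 (criteria violations) | Listed | Not listed |
| Table 14.1.4.3 ("Concomitant Disallowed Medication") and Listing 16.2.4.5 | Included | Not included |
| Per-protocol population (SAP 6.4, 6.5) | Excluded only if the deviation is judged major and affecting the efficacy analysis | No effect |
| ITT efficacy analyses | Unaffected | Unaffected |

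The named outputs are not a complete list. Protocol 16.4 requires collection of deviations from eligibility criteria and concomitant-medication restrictions, so Table 14.1.2.1 and Listing 16.2.2.1 may change too. Table 14.1.1.1 would change if the patient is screened out.

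**The case against.** The strongest reply is that the sentence below the table can be read as a note qualifying the row. It follows the table directly, is specific to CYP3A4 and gives examples, and the prohibition in 9.5.3 covers only CYP2D6 drugs. On that reading the defect is a leftover clause rather than two live rules. The reading is possible, but nothing in the text signals it and it cancels the clause completely, so the text needs repair in any case.

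Second, 9.5.3 is weaker evidence than the sentence in 9.5.2. Its CYP2D6 paragraph also asks for monitoring before it prohibits narrow-index drugs, so monitoring language alone is not permission. That is fair: the explicit conflict is one clause against one sentence, both in 9.5.2. The CYP3A4 paragraph still assumes concurrent use of narrow-window drugs and states no prohibition, so it supports the sentence and not the row.

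Third, practical harm is limited, because the Medical Monitor can be asked and exclusion criterion 11 covers unacceptable risk. Neither says which rule holds, and a site that has read only one of the two texts has no reason to ask.

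Fourth, the affected outputs are descriptive and the number of patients may be zero. This stands, and it limits how serious the point is.

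**Conclusion.** The contradiction is real and the protocol is wrong as written. One clause of one Table 3 row conflicts directly with the sentence below it and does not fit the CYP3A4 paragraph of 9.5.3. The CYP2D6 part of the row is not in conflict.

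The effect is on eligibility, on a safety instruction and on at least three planned outputs: Table 14.1.4.3, Listing 16.2.4.5 and Listing 16.2.3.1. The primary inference is not at risk. The number of affected patients among the approximately 200 planned cannot be derived from the documents.

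The conclusion assumes that *index* and *window* mean the same thing, as the protocol's own usage shows, and that the redacted text after SAP criterion 9 does not settle the matter. The correction should be made, but the point does not threaten the trial's main result.

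**What to change.** Reconcile the closing clause of the Table 3 row, the sentence below it and the CYP3A4 paragraph of 9.5.3 into one rule, using a single term (*index* or *window*) throughout. Which rule applies is for the sponsor's clinical team; this review takes no position on it. Exclusion criterion 9 in both documents takes up the rule by cross-reference, so on the visible text it needs no separate edit.

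Then apply the same rule to the SAP disallowed-medication flag and to the deviation criteria in the BDRM Preparation Plan, which SAP 6.5 already requires, before the blinded review.

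The cost is one protocol clarification and one matching line in that plan, with no added procedures, visits or patients. Because the text governs eligibility and safety, the change may not qualify as an administrative amendment under Protocol 16.6.1. It could then need regulatory and ethics approval before sites apply it.
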